8.1.2 Endpoints? (e.g. clinical records, laboratory markers				

Section 8: Data sources	Yes	No	N/A	Page Number(s)
or values, claims data, self-report, patient interview including scales and questionnaires, vital statistics, etc.)				10
8.1.3 Covariates?				10 - 11
8.2 Does the protocol describe the information available from the data source(s) on:				
8.2.1 Exposure? (e.g. date of dispensing, product quantity, dose, number of days of supply prescription, daily dosage, prescriber)				10
8.2.2 Endpoints? (e.g. date of occurrence, multiple event, severity measures related to event)				10 - 11
8.2.3 Covariates? (e.g. age, sex, clinical and product use history, co-morbidity, co-medications, life style, etc.)				11
8.3 Is a coding system described for:				
8.3.1 Diseases? (e.g. International Classification of Diseases (ICD)-10)				10 + 24-25
8.3.2 Endpoints? (e.g. Medical Dictionary for Regulatory Activities (MedDRA) for adverse events)				
8.3.3 Exposure? (e.g. WHO Drug Dictionary, Anatomical Therapeutic Chemical (ATC) Classification System)				10 + 24-25
8.4 Is the linkage method between data sources described? (e.g. based on a unique identifier or other)				12

Comments:

--

Section 9: Study size and power	Yes	No	N/A	Page Number(s)
9.1 Is sample size and/or statistical power calculated?				12

Comments:

--

Section 10: Analysis plan	Yes	No	N/A	Page Number(s)
10.1 Does the plan include measurement of excess risks?				
10.2 Is the choice of statistical techniques described?				13
10.3 Are descriptive analyses included?				13
10.4 Are stratified analyses included?				13
10.5 Does the plan describe methods for adjusting for confounding?				
10.6 Does the plan describe methods addressing effect modification?				

Comments:

This is a descriptive study so there are no issues of confounding.
--

Section 11: Data management and quality control	Yes	No	N/A	Page Number(s)
11.1 Is information provided on the management of missing data?				
11.2 Does the protocol provide information on data storage? (e.g. software and IT environment, database maintenance and anti-fraud protection, archiving)				13
11.3 Are methods of quality assurance described?				13
11.4 Does the protocol describe possible quality issues related to the data source(s)?				13,14
11.5 Is there a system in place for independent review of study results?				

Comments:

Data are descriptive and missing data is not a concern.
---

Section 12: Limitations	Yes	No	N/A	Page Number(s)
12.1 Does the protocol discuss: 12.1.1 Selection biases? 12.1.2 Information biases? (e.g. anticipated direction and magnitude of such biases, validation sub-study, use of validation and external data, analytical methods)	  	  	  	
12.2 Does the protocol discuss study feasibility? (e.g. sample size, anticipated exposure, duration of follow-up in a cohort study, patient recruitment)				12
12.3 Does the protocol address other limitations?				14

Comments:

Section 13: Ethical issues	Yes	No	N/A	Page Number(s)
13.1 Have requirements of Ethics Committee/Institutional Review Board approval been described?				14
13.2 Has any outcome of an ethical review procedure been addressed?				TBD
13.3 Have data protection requirements been described?				13

Comments:

Section 14: Amendments and deviations	Yes	No	N/A	Page Number(s)
14.1 Does the protocol include a section to document future amendments and deviations?				6

Comments:

Section 15: Plans for communication of study results	Yes	No	N/A	Page Number(s)
15.1 Are plans described for communicating study results (e.g. to regulatory authorities)?				14
15.2 Are plans described for disseminating study results externally, including publication?				14

Comments:

--

Name of the main author of the protocol: \_\_\_\_ [name] DSc

Date: 21/03/2016

Signature: \_\_\_\_\_

### Annex 3. Additional information

#### *Codes for procedures used to identify study patients exposed to iodinated contrast agents*

Procedure codes	CPT and HCPCS	Data source
CT scans with contrast	70470, 70482, 70488, 70491, 70492, 70496, 70498, 71270, 71275, 72126, 72127, 72128, 72129, 72130, 72133, 72191, 72194, 73202, 73206, 73702, 73706, 74170, 74174, 74175,	KPNC data
Left heart catheterization	93452, 93453, 93454, 93455, 93456, 93457	
Ventriculography	93458, 93459, 93460, 93461	
Cardio/ Coronary angiography	93563, 93564, 93565, 93566	

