## **8. Research questions and objectives**

### **8.1 Primary objective**

The goal of this study is to estimate the incidence rate of hypothyroidism, detected in routine clinical practice, in a US-based general population of patients less than 4 years of age during years 2008 - 2015, in the 365 days post exposure to an iodinated contrast agent. .

Hypothyroidism cases will be categorized into “probable iodine-induced hypothyroidism” and “possible alternative etiology” after medical records review.

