#### **9.2.3 Study population**

The study population will be all patients who were under the age of 4 at some time during the years 2008 to 2015 in the US- based KPNC database who had a procedure with iodinated contrast agent. A preliminary search of the data identified around 2300 people under age 4 who had a procedure with iodinated contrast, by searching CPT and HCPCS codes. We will also require that all children in the study were members of KPNC for at least 3 months before the iodinated contrast exposure, except where the child is under 3 months of age at time of initial exposure, and 2 weeks after the exposure. From this population we will exclude all children who had a diagnosis of hypothyroid any time prior to the iodine contrast exposure. We will also exclude those with lab values for low thyroid (TSH > 5 mU/L for children) any time before the

exposure, and those with thyroid replacement therapy, Hashimoto thyroiditis, or congenital hypothyroidism any time prior to the exposure.

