### **9.3.2 Exposure**

Exposure will be identified through CPT codes for procedures that include iodinated contrast agent. The date the procedure was coded will be considered the date of exposure. The majority of these will be CT scans with contrast. We will also identify young children who had a left heart catheterization including cardio-angiography, ventriculography, and coronary angiography. Each child will be followed for up to 365 days after a qualifying exposure (the exposure window).

There will be no differentiation according to any specific brand of contrast agents, considering that there is general agreement that iodine induced hypothyroidism is considered a class-effect of all iodinated contrast agents and not restricted to specific agents

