## **9.9 Limitations of the research methods**

There is access to original clinical records in the KPNC database, thus validation will be possible. However we may miss some children who had procedure using iodinated contrast if the procedures were not coded properly. It is also possible that some children will have undiagnosed hypothyroidism. These will also be missed in this study.

Although most members enroll through their employers, many are members of KPNC through MediCal (a low-income health insurance plan). Analysis of U.S. census data demonstrates that KPNC members are representative of the general population with regard to ethnicity and education and differ only slightly with regard to income, we tend to underrepresent the very rich and the very poor. Members are remarkably similar to the general population in terms of employment status, marital status, screening practices, and prevalence of medical conditions, when compared with population-based data from the California Behavioral Risk Factor Surveillance System.

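### The objective covers any iodinated contrast exposure, but the code list captures only contrast CT and left-heart catheterization/cardiac angiography, so the rate describes a narrower population and earlier unlisted contrast goes unseen.

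*Combined protocol and SAP*

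**What the plan says.** The primary objective (8.1) concerns hypothyroidism "in the 365 days post exposure to an iodinated contrast agent". Section 9.2.3 takes as its population children under 4 "who had a procedure with iodinated contrast agent". The abstract, and the first secondary objective in 8.2, are worded just as generally.

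Section 9.3.2 gives a general rule: "Exposure will be identified through CPT codes for procedures that include iodinated contrast agent". It then names the procedures it has in mind. Of the exposures, "The majority of these will be CT scans with contrast", and in addition: "We will also identify young children who had a left heart catheterization including cardio-angiography, ventriculography, and coronary angiography". It does not separate brands, because it regards iodine-induced hypothyroidism as an effect of the whole class of agents.

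The Annex 3 table, "Codes for procedures used to identify study patients exposed to iodinated contrast agents", puts the rule into operation with four rows: contrast CT, left heart catheterization, ventriculography, and cardio/coronary angiography.

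On missed exposures, Section 9.9 says: "However we may miss some children who had procedure using iodinated contrast if the procedures were not coded properly". Neither the exclusions in 9.2.3 nor the case review in 9.3.3 asks about contrast given before the index procedure.

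**The concern.** The question asked and the exposure measured differ in scope. A child whose only contrast procedure was, say, a venogram meets the wording of 8.1 and 9.2.3 but cannot enter the cohort, even if the procedure was coded correctly. That is a consequence of the list, not of the miscoding that 9.9 describes.

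Three outputs are touched:

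- **The primary rate.** It applies to children with the listed procedures, while the objective and abstract would lead a reader to apply it to iodinated contrast in general.
- **The description of children who have contrast procedures (8.2).** The list fixes in advance which procedure types can appear.
- **The time from exposure to diagnosis (8.2, 9.7).** If an unlisted contrast procedure came before the first listed one, the clock starts late. If TSH rose above 5 mU/L in between, 9.2.3 excludes the child as having earlier thyroid disease, although that rise followed contrast.

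The point concerns procedure types with no row in Annex 3, not the choice of CT codes within the CT row.

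**Working it through.** **Step 1: scope, place by place.**

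| Place | Exposure as worded |
|---|---|
| Abstract, 8.1, 8.2, 9.2.3 | Any iodinated contrast agent or procedure |
| 9.3.2, first sentence | Any procedure that includes contrast, found by CPT code |
| 9.3.2, examples | Contrast CT; left heart catheterization with its angiography |
| Annex 3 | CT (24 codes), left heart catheterization (6), ventriculography (4), cardio/coronary angiography (4): 24 + 6 + 4 + 4 = 38 codes, no other type |
| 9.9 | Loss of exposures through miscoding |

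The CT row ends in a comma, so a code may have been lost from the text. A lost CT code would not add a procedure type.

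**Step 2: look-back.** The pre-exposure exclusions in 9.2.3 are a hypothyroid diagnosis, raised TSH, thyroid replacement, Hashimoto thyroiditis and congenital hypothyroidism. The three-month membership rule is not tied to a contrast-free period, and it is waived below 3 months of age. The review in 9.3.3 looks for earlier thyroid disease and other causes. The list of associated drugs and procedures in Annex 3 contains no contrast procedure. Section 9.2.3 speaks of an initial exposure, which suggests that the first coded procedure is the index, but it is first only among listed codes.

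**Step 3: the plan's figure.** The study size of around 2300 (9.2.3, 9.5) is the count from a preliminary code search. There is no precision target or formula behind it, so there is nothing to reproduce.

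**Step 4: how far the two rates could differ.** The documents give neither input, so both are assumptions:

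- s = share of all contrast-exposed children who had only unlisted procedures, 10-40%;
- RR = their risk relative to captured children, 0.5-3.

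With similar follow-up in both groups:

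all-contrast rate / reported rate = (1 - s) + s × RR

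If the 2300 are the captured children, the number outside the list is 2300 × s / (1 - s).

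| s | Children outside the list | RR = 0.5 | RR = 1 | RR = 2 | RR = 3 |
|---|---|---|---|---|---|
| 10% | 256 | 0.95 | 1.00 | 1.10 | 1.20 |
| 20% | 575 | 0.90 | 1.00 | 1.20 | 1.40 |
| 40% | 1533 | 0.80 | 1.00 | 1.40 | 1.80 |

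The extremes are 0.6 + 0.4 × 0.5 = 0.80 and 0.6 + 0.4 × 3 = 1.80. The range includes 1, so not even the direction is fixed. At RR = 1 the rate is unchanged whatever the share.

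**Step 5: day 0.** Suppose an unlisted procedure took place d days before the first listed one. The recorded time to diagnosis is then d days shorter than the time since first contrast. Any TSH above 5 mU/L recorded within those d days removes the child from the cohort. The documents give no frequency for this sequence, so its effect cannot be calculated.

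**The case against.** The strongest reply is that the restriction is not hidden. Section 9.3.2 names contrast CT and "left heart catheterization including cardio-angiography, ventriculography, and coronary angiography", and Annex 3 agrees with it. A descriptive study may confine itself to named procedures, and the rate among captured children is still a valid rate for them. The documents also do not show that the omitted procedures are common at this age. All of this stands. It makes the matter one of stated scope and of day 0, not of a wrong calculation. It does not remove the mismatch, because the objective, abstract and limitations do not carry the restriction.

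A reader might infer more than the documents support:

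- **That 9.9 presents miscoding as the sole way to miss exposures.** It names miscoding as one limitation and does not say that there are no others.
- **That infants with heart disease are under-represented.** The rationale singles out neonates and preterm infants and does not mention congenital heart disease, and three of the four Annex 3 rows are cardiac.
- **That right-heart angiography is left out.** The cardio/coronary row is not labelled as left-sided, and the codes carry no descriptors, so the documents do not settle this.
- **That the missing look-back follows from the list's scope.** No check for earlier contrast of any type is described. The narrow list adds to that gap but does not create it.

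It is also fair to say that widening the cohort has a cost. Each added potential case needs review of the electronic record and the original notes (9.3.3, 9.8), and Section 6 places data collection in October-November 2016 with a preliminary report on 22 December 2016.

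**Conclusion.** The point holds as one of scope and of index date. As written, the study will estimate the rate after contrast CT or left-heart catheterization/cardiac angiography, while the objective and abstract state it for iodinated contrast in general.

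It would go too far to say that the reported rate is too low, or that acute cases are being removed at baseline. The first would need a share and a risk ratio that the documents do not give; under the assumed ranges (10-40%, 0.5-3) the all-contrast rate is 0.80-1.80 times the reported one. The second needs an unlisted procedure, then a recorded thyroid abnormality, then a listed procedure in the same child, which may happen but at an unknown frequency.

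The conclusion rests on reading Annex 3 as the complete list of qualifying procedure types, which its title and 9.3.2 support. That other catheter angiography, venography and urography can use iodinated contrast is general knowledge; the documents do not mention them. The change is worth making because it alters what the study can claim, and most of it is free.

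**What to change.** 1. **State the scope.** Word the objective, the abstract and the report's conclusion as the rate after contrast-enhanced CT or left-heart catheterization/cardiac angiography. Add to 9.9 that correctly coded contrast procedures outside Annex 3 are not captured. This costs nothing.

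2. **Run a flag-only query.** Section 9.6 already provides for a data set of all children under 4 at KPNC. Search it for other iodinated-contrast procedure codes before the thyroid exclusions are applied. Report how many children had only unlisted procedures, how many cohort members had contrast before their index date, and how many children excluded for earlier thyroid abnormality had unlisted contrast before it. Then repeat the rate and the time to diagnosis with the children who had earlier contrast first excluded, and then re-dated to the earlier procedure with eligibility reassessed at that date. The cost is a small amount of programming and analysis. The query also replaces the assumed share in the range above with a count.

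3. **Optional: add the procedures as exposures, reported by type.** This would match the present objective, but it adds case-record review and changes the count of around 2300. It is not needed if 1 and 2 are done.

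### The Annex 3 contrast-CT code list treats code families inconsistently: on the usual CPT scheme, still to be confirmed, it omits nine single-phase contrast codes and includes one non-contrast code

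*Combined protocol and SAP*

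**What the plan says.** Section 9.2.3 defines the cohort as all KPNC children under 4 in 2008–2015 with an iodinated contrast procedure, subject to membership and prior-thyroid exclusions. It reports that a preliminary search "identified around 2300 people under age 4 who had a procedure with iodinated contrast, by searching CPT and HCPCS codes". Section 9.5 repeats the 2300 without a breakdown.

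Section 9.3.2 gives the exposure rule: "Exposure will be identified through CPT codes for procedures that include iodinated contrast agent". Of these procedures it says: "The majority of these will be CT scans with contrast".

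The codes are in Annex 3, in the table titled "Codes for procedures used to identify study patients exposed to iodinated contrast agents". The contrast-CT row reads "70470, 70482, 70488, 70491, 70492, 70496, 70498, 71270, 71275, 72126, 72127, 72128, 72129, 72130, 72133, 72191, 72194" and continues "73202, 73206, 73702, 73706, 74170, 74174, 74175", which makes 24 codes. Three cardiac rows follow. No code has a descriptor, body region or contrast status. The code column is headed for both CPT and HCPCS, but no visible entry is identified as HCPCS.

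**The concern.** Annex 3 is the operational entry rule, so an error in it changes who is in the cohort. The contrast-CT row matters most because the plan expects most exposures to come from it. The row is in ascending order, yet it lists runs of neighbouring codes for some families and a single code for others, with no stated reason.

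Two errors are possible. Children with a properly coded contrast CT could be missed because the code is not on the list. Children with a non-contrast CT could be followed as exposed.

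The planned safeguards do not cover the first error:

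- Section 9.8 checks a random sample of records from the study population. That may find wrongly included children, but not children who were never selected.
- The record review in section 9.3.3 is limited to potential cases and looks at thyroid status.
- Section 9.9 acknowledges missed exposures only where a procedure was miscoded. A correctly coded procedure left off the list is a different loss.
- The ENCePP checklist (section 12) marks selection and information bias as not applicable.

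**Working it through.** **Reproducing the plan's figure.** The 2300 is a database count. No counts per code are given, so it cannot be reproduced.

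**What the list alone shows.** Of the 24 CT codes, the consecutive runs are 70491–70492, 72126–72130 and 74174–74175. All others stand alone.

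**Assumption from outside the documents.** CPT codes for CT come in threes per body region: without contrast, with contrast, without then with. The region names below rest on the same assumption. It must be checked against the code books for each study year.

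| Family | Without | With | Without then with |
|---|---|---|---|
| Head | – | 70460 absent | 70470 listed |
| Orbit/ear | – | 70481 absent | 70482 listed |
| Maxillofacial | – | 70487 absent | 70488 listed |
| Neck | – | 70491 listed | 70492 listed |
| Chest | – | 71260 absent | 71270 listed |
| Cervical spine | – | 72126 listed | 72127 listed |
| Thoracic spine | **72128 listed** | 72129 listed | 72130 listed |
| Lumbar spine | – | 72132 absent | 72133 listed |
| Pelvis | – | 72193 absent | 72194 listed |
| Upper extremity | – | 73201 absent | 73202 listed |
| Lower extremity | – | 73701 absent | 73702 listed |
| Abdomen | – | 74160 absent | 74170 listed |

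(– means not listed.)

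Listed by position: 1 of 12 in the first column, 3 of 12 in the second, 12 of 12 in the third. Sum: 1 + 3 + 12 = 16. The other 8 codes (70496, 70498, 71275, 72191, 73206, 73706, 74174, 74175) fall outside these triplets: 16 + 8 = 24.

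The inconsistency needs only that a position means the same in every family. If the second position is a contrast scan, nine are missing. If it is not, three are wrongly present. Likewise, the first position is listed once and left out eleven times.

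**Could a cut-off table explain it?** The row ends in a comma after 74175, so later codes may be lost. For that reason the combined abdomen-pelvis codes (74176–74178) are not counted here. Eight of the nine absent codes would fall between listed codes, and 70460 would come immediately before the first listed code, so text lost at the end explains none of them.

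**Effect of wrongly included children.** Let *f* be the share of person-time that is unexposed and *r* the unexposed rate divided by the exposed rate. Then

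observed rate / exposed rate = 1 − *f*(1 − *r*).

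The documents give neither quantity. As pure illustration, with *r* = 0 and equal follow-up:

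| *f* (assumed) | Children of 2300 | Ratio |
|---|---|---|
| 1% | 23 | 0.99 |
| 5% | 115 | 0.95 |
| 10% | 230 | 0.90 |
| 20% | 460 | 0.80 |

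Only one of the 24 CT codes is in question, and its frequency under age 4 is not stated.

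**Effect of missed children.** Let *m* be the share of exposed person-time missed and *ρ* the rate in missed children divided by the rate in captured children. Then

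captured rate / rate in all exposed = 1 / (1 − *m* + *mρ*).

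If *ρ* = 1 the ratio is 1 for any *m*: precision is lost but there is no bias. If *ρ* < 1 the reported rate is too high, and if *ρ* > 1 too low. The plan leaves *ρ* ≠ 1 open: section 9.7 names type of procedure among possible risk factors, and section 7 says the free iodide given depends on total dose.

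**The case against.** The strongest objection is that the documents never say what any code means. The omission of single-phase scans and the status of 72128 both come from the CPT scheme. That is correct, and it is why the conclusion is conditional. What stands without the code book is the uneven pattern in a list meant to contain contrast CT only, and the lack of descriptors by which a reader could check it. That pattern is enough to require the check.

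Several stronger readings are tempting and are not supported:

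- *A child with an ordinary contrast CT never enters.* Such a child can still qualify through another listed CT or cardiac code. Only children whose sole contrast exposure carried an omitted code are lost.
- *Unexposed children are certainly in the cohort.* That requires 72128 to have been used under age 4. The random record check in section 9.8 might also catch some of them.
- *The true exposed count can be scaled up from 2300.* If 25%, 50% or 75% were missed, 2300/(1 − share) gives 3067, 4600 or 9200. No such share is in the documents, section 9.2.3 does not say that the 2300 came from exactly the Annex 3 list, and a share of scans is not a share of children.
- *The rate is biased.* Omission biases it only if risk differs between captured and missed children, which the plan treats as possible and does not establish.
- *The cardiac codes have a similar gap for some study years.* The documents give no validity dates for any code, so nothing is claimed here.

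**Conclusion.** The concern holds conditionally. The inconsistent treatment of code families in the entry list is visible in Annex 3. If the without / with / without-then-with scheme is confirmed for 2008–2015, the list omits the single-phase contrast code in 9 of 12 families and includes one non-contrast code. The cohort would then not be all exposed under-4s, as section 9.2.3 intends, and any child entering only through 72128 would dilute the rate.

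The numbers of children missed and wrongly included, and the direction of any bias from omission, cannot be derived from the documents. Separately, and without the code book, the 2300 cannot be traced: section 9.2.3 refers to HCPCS codes, none is identified in the visible table, and no counts by code are given. This should be settled before the cohort is fixed, because no later step in the plan recovers missed children.

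**What to change.** Before the cohort is finalised:

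1. Add to Annex 3 the descriptor and contrast status of every listed code, checked against the CPT code book for each study year.
2. On confirmation, add 70460, 70481, 70487, 71260, 72132, 72193, 73201, 73701 and 74160, and delete 72128. Do neither before the check.
3. List the HCPCS codes that section 9.2.3 says were searched.
4. Re-run the query and replace the figure of about 2300 in the abstract and in sections 9.2.3 and 9.5 with the resulting count by code family and year.

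The cost is a code-list edit and one query. The cohort may grow, possibly by a good deal, with more potential cases to review, and the 2300 will change. Section 6 places data collection in October and November 2016 and the protocol is dated 11 October 2016, so extraction may already have started. If so, the cohort has to be rebuilt, and record review is needed for any newly identified potential cases.
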